2.7.4 Other safety data

[figure not shown]
2.7.4.1 ECG and cardiac imaging data

ECG results will be listed.

2.7.4.2 Vital signs

Observed value, change, and percent change from baseline in vital signs (pulse rate, [REDACTED], [REDACTED]) will be summarized descriptively at each analysis visit (including Day 330/Last Visit) by treatment group.

10

2.8 Pharmacokinetic endpoints

Not applicable.

2.9 PD and PK/PD analyses

Not applicable.

2.10 Patient-reported outcomes

See Section [2.12](#).

2.11 Biomarkers

See Section [2.6](#).

2.12 Other Exploratory analyses

The exploratory efficacy variables are the following:

8. Cardiovascular death (yes, no)
9. Non-fatal MI (yes, no)
10. Resuscitated cardiac arrest (yes, no)
11. Non-fatal ischemic stroke (yes, no)
12. Composite MACE (cardiovascular death, non-fatal MI, resuscitated cardiac arrest, or non-fatal ischemic stroke) (yes, no)

[REDACTED]

[REDACTED]

[REDACTED]

Exploratory efficacy variables 8-12 will be summarized descriptively by total number of events and number and percentage of subjects with any event for each treatment group. In addition, a time-to-event analysis will be carried out. Time to first occurrence of any event in the composite MACE as well as time to first occurrence of each of its components will be derived as study day of onset of the corresponding TEAE, imputing for partially missing dates as needed. Adverse events with missing onset date will not be considered in the time-to-event analysis. Cox proportional hazards models will be used to estimate the corresponding hazard ratios of inclisiran + usual care over usual care with associated 95% confidence intervals. Treatment and baseline LDL-C will be used as explanatory variables in the Cox proportional hazards models. Observation time for participants without the respective event will be censored at their end of study date (date of last participation) or date of death, as applicable.

[REDACTED]

[figure not shown]
[REDACTED]

[REDACTED]

Table 2-6 MACE Definitions (using TEAEs only)

Category	Details
Cardiovascular death	(1) Fatal SAEs in "Cardiac disorders" SOC (2) Fatal SAEs in "General disorders and administration site conditions" SOC: PTs "Death", "Sudden cardiac death", "Cardiac death", "Apparent death" (3) Central nervous system haemorrhages and cerebrovascular accidents (HLT), fatal events only
Non-fatal MI	Myocardial infarction (SMQ, broad and narrow search), non-fatal events only, excluding PT "Blood creatine phosphokinase increased"
Resuscitated cardiac arrest	PT "Cardiac arrest", non-fatal events only

Non-fatal ischemic stroke	PT "Ischaemic stroke", non-fatal events only
---------------------------	--

A 7x7 grid of black bars on a white background. The bars are arranged in a pattern where the width of each bar in a row is the sum of the widths of the bars in the row above it. The widths of the bars in each row are: Row 1: 1, 1, 1, 1, 1, 1, 1; Row 2: 1, 1, 1, 1, 1, 1, 1; Row 3: 1, 1, 1, 1, 1, 1, 1; Row 4: 1, 1, 1, 1, 1, 1, 1; Row 5: 1, 1, 1, 1, 1, 1, 1; Row 6: 1, 1, 1, 1, 1, 1, 1; Row 7: 1, 1, 1, 1, 1, 1, 1.

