2.1.1 General definitions

Study treatment

The following are the investigational treatments:

- Inclisiran (KJX839), 284 mg, 1.5 ml liquid in a single-use prefilled syringe (PFS) for s.c. administration plus usual care
- Usual care alone

The following treatment labels will be used for all tables, listings and figures:

- Inclisiran + Usual Care
- Usual Care

Study treatment start and end date

Study treatment start date is defined as the first date when a non-zero dose of study drug is administered for the inclisiran + usual care group. If a participant, who is randomized to the inclisiran + usual care group, does not take any study drug then treatment start date will be the randomization date.

For the usual care alone group the study treatment start date will be the randomization date.

“Day 1” will be used to identify study treatment start date for both treatments.

Study treatment end date is defined as the treatment phase completion date recorded on the “Treatment Disposition” CRF for inclisiran + usual care participants. For the usual care alone group, the study treatment end date is the last recorded contact/participation date in the database.

Study start and end date

Study start date is defined as the first date when a non-zero dose of study drug is administered for the inclisiran + usual care group. If a participant, who is randomized to the inclisiran + usual care group, does not take any study drug then study start date will be the randomization date.

For the usual care alone group the study start date will be the randomization date.

Study end date is defined as the date of last recorded contact/participation date in the database.

Duration of exposure to inclisiran

For the inclisiran + usual care group, duration of exposure to inclisiran (in days) is defined as the number of days from Day 1 to the study *treatment* end date. Duration of exposure will not be defined for the usual care alone group.

Planned and actual treatment definitions

The following definitions will be used for planned and actual treatment.

Table 2-1 Planned and Actual Treatment Definitions

Randomized Treatment Group	Inclisiran Use Scenario During Study (Inclisiran Use Recorded as Study Treatment or Concomitant Medication)	Planned Treatment	Actual Treatment
Inclisiran + Usual Care	Received at least one dose of inclisiran	Inclisiran + Usual Care	Inclisiran + Usual Care
Inclisiran + Usual Care	Never received inclisiran	Inclisiran + Usual Care	Usual Care

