2.7.1 Adverse events (AEs)

The Medical Dictionary for Regulatory Activities (MedDRA) dictionary will be used for coding AEs, and up-versioning will be applied during the course of study. The final MedDRA version used in this study will be v27.0. Partially missing AE dates will be imputed following Appendix 5.1.2. An AE (classified as preferred term) occurring during the treatment period will be counted as a treatment-emergent AE (TEAE) either if it is not present at Day 1 before treatment or if it is present before treatment but increased in severity during the treatment period. Therefore, all recorded AEs with onset on or after the study treatment start date will be counted as TEAE. In case the AE date values do not allow unequivocally allocating an AE record to TEAE or non-TEAE, the AE will be considered as TEAE in the statistical analysis. The following summary tables will be presented:

- Overall Summary of TEAEs
- TEAEs by System Organ Class (SOC) and Preferred Term (PT)
- TEAEs by PT
- Common ($\geq 3\%$ within either treatment group) by PT
- TEAEs by SOC, PT, and Severity
- TEAEs by SOC, PT, and Relationship to Study Treatment
- Related TEAEs by SOC, PT, and Severity
- Treatment Emergent Serious AEs (TESAEs) by SOC and PT
- TESAEs by PT
- TESAEs by SOC, PT, and Severity
- TESAEs by SOC, PT, and Relationship to Study Treatment
- Related TESAEs by SOC, PT, and Severity
- TEAEs Leading to Withdrawal of Study Treatment by SOC and PT
- TEAEs with a Fatal Outcome by SOC and PT

If more than one event occurred with the same PT for the same participant, the participant will be counted only once for that PT using the most severe or related occurrence for the summary by severity, or relationship to study drug, respectively.

Missing severity and relationship will not be imputed and will be identified as 'missing' in the tables.

For common (3% within either treatment group) TEAEs, serious TEAEs and TEAEs leading to withdrawal of study treatment, risk ratios along with 95% confidence intervals will be presented to compare treatment groups with respect to risk.

For tables presented by SOC and PT, system organ classes are sorted alphabetically and within each system organ class, the preferred terms are sorted in descending order of total frequency.

For tables presented by PT, preferred terms are sorted in descending order of total frequency.

Listings will be presented for participants with SAEs and AEs leading to discontinuation of study treatment.

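### SAP 2.12 times cardiovascular death at onset of the fatal SAE instead of at death, and a death with no recorded SAE onset date drops out of the Cox model

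*SAP*

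**What the plan says.** SAP 2.12 plans Cox models, adjusted for baseline LDL-C, for composite MACE and for each of its four components. One timing rule covers them all: the time "will be derived as study day of onset of the corresponding TEAE, imputing for partially missing dates as needed". Events with no onset date are left out of this analysis. Participants without the event in question "will be censored at their end of study date (date of last participation) or date of death, as applicable".

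Table 2-6 finds cardiovascular death by MedDRA search. Its first criterion is "Fatal SAEs in 'Cardiac disorders' SOC"; the others are fatal events under a few death-related preferred terms and fatal cerebrovascular events. The MI, cardiac arrest and stroke rows take non-fatal events only. The table title carries the limit "MACE Definitions (using TEAEs only".

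SAP 2.7.1 defines treatment-emergent: "all recorded AEs with onset on or after the study treatment start date will be counted as TEAE". It also admits events present before treatment that then worsen, and it resolves unclear dates in favour of inclusion.

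**The concern.** Onset is the natural date for a non-fatal infarction, arrest or stroke. It is not the date of a death. Because the fatal SAE is the event record, its onset becomes the time of cardiovascular death, and a participant can leave that risk set while still alive. The first criterion spans a whole system organ class, so it is not confined to sudden events; a cardiac failure that ends in death months later qualifies.

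The missing-onset exclusion raises a second problem. A death has a date of its own, yet the analysis discards it if the onset of the underlying event was not recorded. Few cardiovascular deaths may occur, so a single lost one can change the reported hazard ratio visibly.

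**Working it through.** The documents give no event count, rate, hazard ratio or power for this endpoint, so there is no figure to reproduce. The check follows the rules through SAP 2.1.1, 2.7.1, 2.12 and 5.1.2.

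**1. Which date enters the model.** Event: the fatal SAE (Table 2-6). Event time: its onset day (2.12). No visible rule substitutes the date of death, although the censoring rule uses that date. The error is

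lag = study day of death − study day of SAE onset.

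It is zero for a sudden death. In a constructed case with onset on Day 20 and death on Day 300, it is 300 − 20 = 280 days.

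**2. Partial onset dates.** Study day = event date − treatment start date + 1 (2.1.1). Take treatment start 10 March 2022 and death 20 November 2022, which gives 255 + 1 = Day 256.

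| Recorded onset | Rule in 5.1.2 | Imputed event day | Days before death |
|---|---|---|---|
| 2022 only | case (B), start reference | Day 1, if the reference is treatment start | 256 − 1 = 255 |
| November 2022 | case (A), first of month | Day 237 | 256 − 237 = 19 |

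The first row needs its condition. Section 5.1.2 sets the start reference to treatment start when the end date is partial and on or after treatment start, or the event is ongoing. It gives no start reference when the end date is complete and on or after treatment start, which is the usual situation for a fatal event.

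**3. Missing onset.** Completely missing start dates are not imputed (5.1.2), and 2.12 removes such events from the time-to-event analysis. The participant then has no event in the model and is apparently censored at the date of death. The same death can still enter the descriptive count, because 2.7.1 treats unclear dates as treatment-emergent. The table and the Cox model could therefore differ by that death.

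**4. Effect of re-dating on the hazard ratio.** This is an illustration on assumptions that are not in the documents: 192 participants per arm followed for 330 days, no treatment effect, no earlier censoring, exponential onset-to-death lag with the same mean in both arms, no covariate. Each scenario used 300 simulated trials; trials with no death in one arm were set aside. The Cox model was fitted once with death dates and once with onset dates.

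| Death risk | Mean lag | Trials used | Mean deaths | Median HR change | Largest HR change |
|---|---|---|---|---|---|
| 1% | 7 days | 229 | 4.7 | 0.0% | 0.3% |
| 1% | 30 days | 201 | 4.6 | 0.0% | 0.7% |
| 3% | 7 days | 298 | 11.4 | 0.0% | 0.3% |
| 3% | 30 days | 300 | 11.5 | 0.1% | 0.7% |

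The change is small because the Cox estimate depends on the make-up of the risk set at each event. With few deaths and equal follow-up, that make-up hardly differs between the two dates.

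**5. Effect of losing one death.** With equal arms and similar follow-up, HR is roughly the ratio of death counts. Starting from d deaths split equally and dropping one from the inclisiran arm, HR ≈ (d/2 − 1)/(d/2).

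- d = 4: (2 − 1)/2 = 0.5
- d = 12: (6 − 1)/6 = 0.83

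Dropping the death from the usual-care arm instead gives 2/1 = 2.0 and 6/5 = 1.2.

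**6. The treatment-emergent limit.** The definition has no end cut-off, so deaths late in follow-up or after stopping inclisiran are kept. The clock also starts without a dose where needed: "For the usual care alone group the study treatment start date will be the randomization date", and the same date serves for inclisiran-arm participants never dosed. A death after Day 1 is lost this way only if the fatal event began between consent and Day 1, stayed one record, and was not classed as worsened.

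**The case against.** The strongest reply is that the practical effect is close to nil. The endpoint is exploratory, with no alpha, power or decision rule attached. Several listed terms, such as sudden cardiac death, have almost no lag. The 280-day case is constructed, and step 4 supports the view that re-dating barely moves the estimate. All of that stands, and it limits the point to a minor correction.

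For the composite, onset timing can be defended. If an infarction on Day 20 leads to death on Day 50, Table 2-6 admits it only as a cardiovascular death, so using the date of death would put the first MACE on Day 50 although the infarction came on Day 20. This also stands; it calls for an explicit composite rule, not for the date of death throughout.

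A reader might infer that limiting MACE to treatment-emergent events loses deaths in number. The documents do not support that. Step 6 shows how narrow the route is. Protocol 5.2 also excludes a recurrent ACS within 2 weeks before randomization, Protocol 10.1.1 sends conditions present at consent to medical history, and the death listing in SAP 2.7.2 carries no such limit. A reader might also infer that events and censoring run on inconsistent clocks. They do not: both count from treatment start, and censoring at death applies to participants without the event being modelled, for example a non-cardiovascular death in the cardiovascular-death model.

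Finally, parts of SAP 2.12 are redacted, so a further handling rule there cannot be excluded.

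**Conclusion.** On the visible text, the point holds for one component and one exclusion. Cardiovascular death takes the onset day of the fatal SAE and is too early by the onset-to-death lag. A fatal SAE without an onset date is left out of the Cox model even when the date of death is known.

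The expected effect of the dating rule on the hazard ratio is small: at most 0.7% in the assumed scenarios, which did not model loss to follow-up or lags that differ by arm. A dropped death has a larger effect, about 1.0 to 0.5 with four deaths and 1.0 to 0.83 with twelve, both assumed totals. How often either would happen cannot be derived from the documents.

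The wider claim that MACE as a whole is dated too early is not supported: the non-fatal components are properly timed at onset, and the date for a fatal infarction or stroke in the composite is arguable. The primary and secondary analyses are untouched.

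**What to change.** In SAP 2.12:

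- Time the cardiovascular-death component by the date of death, including when the SAE onset date is missing or partial, and confine the missing-onset exclusion to the non-fatal components.
- State which date a fatal event takes in the composite. If onset is kept for any fatal event there, say that the date of death is used when onset is missing, and complete the start-reference rule in SAP 5.1.2 for events with a full end date on or after treatment start.
- Keep onset timing for non-fatal MI, resuscitated cardiac arrest and non-fatal ischemic stroke.

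Optionally, add a clause saying whether an event that began before Day 1 and proved fatal afterwards counts as worsened.

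The cost is a few sentences and a small programming change. No new data are needed, since the censoring rule already relies on the date of death.

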Participants may be seen at any time for an unscheduled visit, e.g., if they experience deterioration or AEs that in the opinion of the Investigator/qualified site staff requires closer monitoring. The assessment(s) performed at an unscheduled visit must include at a minimum: an assessment of concomitant medications, vital signs, and an AE/SAE assessment. Any additional assessments performed are at the Investigator/qualified site staff's discretion.

Table 8-1 Assessment Schedule

Period	Screening	Treatment ¹			Unplanned	
Visit Name	Visit 1	Baseline/Visit 2	Visit 3	Visit 4	EOS/Visit 5	Unscheduled Visit
Days	-30 to -1	0	90	270	330	-
Informed Consent	Х					
Inclusion / Exclusion criteria	Х	X				
Physical Examination	S		S	S	S	
Demography	Χ					
Medical History	Χ					
ACS Medical History	Χ					
Statin Intolerance Medical History	X					
Height and Weight ²	Χ	X	X	X	Χ	
Pulse Rate	X	X	X	X	Χ	X
Blood Pressure	Χ	X	Х	Х	X	X
Prior/Concomitant medications ³	Х	X	X	Х	Х	Х
Surgical / Medical procedures	Х	Х	Х	Х	Х	Х
Urinalysis		X			Χ	
Pregnancy and assessments of fertility ⁴	Х	х	х	Х	Х	
Hematology	Х	Х			Х	
Full Clinical Chemistry		Х				
Limited Chemical Chemistry	Х		X	Х	Х	
Hepatitis Markers	Х					
Lipids and lipoproteins ⁵	Х	Х	Х	Х	Х	
Coagulation	Х	Х				
Biomarker-Lipoprotein(a)		Х	Х	Х	Х	

Period	Screening	Treatment ¹			Unplanned	
Visit Name	Visit 1	Baseline/Visit 2	Visit 3	Visit 4	EOS/Visit 5	Unscheduled Visit
Days	-30 to -1	0	90	270	330	-
Electrocardiogram (ECG)	Х					
Randomization		X				
Inclisiran Dose Administration		X	Х	Х		
IRT Transaction	Х	X	Х	Х	X	
Injection Site Reaction Assessment		X	Х	Х	X	
Clinical Outcome Assessment(s)		Х	X	Х	X	
Adverse Events	X	X	X	Х	X	Х

XAssessment to be recorded in the clinical database or received electronically from a vendor

SAssessment to be recorded in the source documentation only

¹Due to a Public Health Emergency, if participant is unable to attend in-person visit, phone or virtual visit is an acceptable alternative. At home visits by site staff or a nursing service may be used to assist with blood draws and/or study medication administration if required at this visit.

²Height only to be performed at Visits 1 and 2

³ 30 days prior to randomization

⁴All female participants of childbearing potential will have a serum pregnancy test (hCG) performed at Visit 1 (central lab). A urine pregnancy test will be conducted at the local site for remaining visits.

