8.5.1 Clinical Outcome Assessments (COAs)

Clinical Outcome Assessments refer to the assessment (investigator determination) of major adverse cardiovascular events (MACE) during the trial (incidences of cardiovascular death, non-fatal MI, resuscitated cardiac arrest, or non-fatal ischemic stroke).

[figure not shown]

[figure not shown]

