Objective(s)	Endpoint(s)

• To assess overall safety and tolerability of inclisiran	
• Discontinuation of statin therapy (i.e., no statin use \geq 30 days before the end-of-study visit) (yes, no)• Adverse events
Exploratory objective(s)	Endpoint(s) for exploratory objective(s)

• To assess major adverse cardiovascular events (MACE) (investigator determination) in the inclisiran + usual care group compared to usual care group at Day 330	
• Cardiovascular death (yes, no)• Non-fatal MI (yes, no)• Resuscitated cardiac arrest (yes, no)• Non-fatal ischemic stroke (yes, no)• Composite MACE (cardiovascular death, non-fatal MI, resuscitated cardiac arrest, or non-fatal ischemic stroke) (yes, no)

Note that endpoints identified as “absolute” change from baseline correspond to values that are calculated as a change from baseline (post-baseline value minus baseline value).

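### The SAP builds MACE from MedDRA term lists although it is defined by investigator determination; the visible text does not reconcile the two, and the lists can miscount strokes and deaths

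*SAP*

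**What the plan says.** Protocol 8.5.1 reads: "Clinical Outcome Assessments refer to the assessment (investigator determination) of major adverse cardiovascular events (MACE) during the trial". The SAP's exploratory objective (1.2) uses the same basis: "To assess major adverse cardiovascular events (MACE) (investigator determination) in the inclisiran + usual care group compared to usual care group at Day 330". Protocol Table 8-1 has a Clinical Outcome Assessment row marked for the clinical database or a vendor transfer at Visits 2 to 5.

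SAP 2.12 derives the components from adverse event coding. Table 2-6 is titled "MACE Definitions (using TEAEs only"). Its rules are:

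- Cardiovascular death: fatal SAEs in the cardiac system organ class; fatal SAEs coded to four listed preferred terms in the general disorders class, one of which is Death; and "Central nervous system haemorrhages and cerebrovascular accidents (HLT), fatal events only".
- Non-fatal MI: "Myocardial infarction (SMQ, broad and narrow search), non-fatal events only, excluding PT" for raised blood creatine phosphokinase.
- Resuscitated cardiac arrest and non-fatal ischemic stroke: one preferred term each, non-fatal events only.

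Variables 8 to 12 are summarized as counts and percentages, then analysed by Cox models with 95% confidence intervals. Event time is the onset day of the matching adverse event. Partial dates are imputed, but "Adverse events with missing onset date will not be considered in the time-to-event analysis".

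**The concern.** An investigator's judgement that an event was a MACE and a search on its MedDRA code can disagree in either direction. The visible text names no tie-break and gives the investigator's assessment no role in the derivation. Following Table 2-6 to the letter can therefore lose an ischemic stroke because of the term it was coded to, and can add a death as cardiovascular because of the term it was coded to. Separately, the descriptive table and the Cox model can rest on different sets of events. At stake are the counts for variables 8 to 12 and their hazard ratios, which would no longer answer the objective in SAP 1.2.

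**Working it through.** The plan states no MACE rate, event count or power, so there is no figure to reproduce. The check is mainly a comparison of rules.

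**Rule by rule**

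| Event | Stated endpoint | SAP rule | Result |
|---|---|---|---|
| Non-fatal ischemic stroke coded to another term | Counts (variable 11) | One preferred term only | Not counted |
| Non-fatal CNS haemorrhage | Does not count | Not in the list | Correctly left out |
| Fatal CNS haemorrhage | Can be a cardiovascular death | Whole high-level term | Counted; consistent |
| Fatal SAE coded to Death | Depends on the investigator's determination | Always cardiovascular death | Code overrides judgement |

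**Undated events**

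1. SAP 5.1.2 does not impute a completely missing start date.
2. SAP 2.7.1 treats an event whose dates leave its status ambiguous as treatment-emergent, so it remains eligible for Table 2-6.
3. The descriptive summary in 2.12 has no date exclusion, so the event is counted there.
4. The Cox analysis leaves it out. Participants without the event are censored at end of study or death. Whether someone whose only event is undated belongs to that group is not stated. If so, a death whose event has no onset date would be censored at the date of death, because time runs from event onset.

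**Scale, under an assumed incidence**

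Assume 2% to 10% of the 384 randomized participants have a MACE; the documents support no particular value.

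- Events D: 384 × 0.02 = 7.7; 384 × 0.10 = 38.4.
- Share of one event: 1/7.7 = 13%; 1/38.4 = 2.6%.
- With 1:1 allocation, SE(log HR) ≈ 2/√D, so the 95% interval is the hazard ratio multiplied and divided by exp(1.96 × 2/√D). This factor is 4.11 at D = 7.7 and 1.88 at D = 38.4.
- If 10% to 20% of events were lost (also assumed), the factor becomes 4.44 to 4.86 at 2% incidence and 1.95 to 2.03 at 10%.
- Power for an assumed hazard ratio of 0.7 at two-sided 5% is about 7% with 7.7 events and 20% with 38.4, before any loss.

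Lost events widen an already wide interval only modestly. The more relevant effect is that, with so few events, reclassifying one or two visibly changes the counts.

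**The case against.** Adverse events are themselves identified by investigators and recorded as diagnoses where possible (Protocol 10.1.1), so investigator determination may only mean not centrally adjudicated. Redacted blocks surround Table 2-6 and could hold a linking rule. This stands in part: one cannot say that the SAP discards the investigator's view, only that the visible text does not reconcile it with the lists. Counting a death coded only as Death as cardiovascular may also be a deliberate convention, but the SAP does not say so.

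A reader might infer that fatal and non-fatal stroke should share one term group. The endpoints do not support that. Cardiovascular death is not restricted to ischemic causes, whereas variable 11 is ischemic stroke. A common group would put haemorrhages into variable 11 or remove haemorrhagic deaths from variable 8. The defect is the single preferred term.

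A reader might infer from Table 8-1 that a separate MACE form is completed at each visit. This is not shown. The protocol glossary defines a Clinical Outcome Assessment more broadly, the row is also marked at baseline, text after 8.5.1 is missing, and the CRF is not among the documents.

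A reader might fault SAP Section 4 for not listing the derivation as a change. That is weak: the visible text of Protocol 12.6 lists the variables without a derivation or model, and the SAP's document history does disclose the added time-to-event analyses.

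Finally, start dates are part of the required adverse event record (Protocol 10.1.1) and missing values are queried (Protocol 11.1), so a wholly undated MI, stroke or death should be rare.

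**Conclusion.** The point holds as a mismatch between the definition of MACE and its derivation, with three specific consequences: non-fatal ischemic strokes coded elsewhere are missed, deaths coded to Death are always counted as cardiovascular, and undated events appear in the counts but not in the Cox analysis.

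Two stronger statements are not supported. Undated events are not dropped from MACE altogether; only the time-to-event analysis omits them. And censoring such participants as event-free is a natural reading of the censoring rule, but the SAP does not state it.

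The effect is confined to exploratory variables 8 to 12; no primary or secondary conclusion depends on them. Any percentage of events lost is an assumption, as are the incidence range and hazard ratio used above. With at most about 20% power on those assumptions, the MACE comparison is descriptive under any definition. That limits the importance of the point but does not remove the need for a consistent count.

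**What to change.** 1. Check the CRF version cited in the SAP. Where it captures the investigator's MACE classification, make that the source for variables 8 to 12 and keep Table 2-6 as a case-finding or sensitivity search. Where it does not, have the investigator-reported diagnosis confirm each term-search hit, including deaths coded to Death. Say which source prevails in a disagreement.
2. Replace the single preferred term for variable 11 with a pre-specified group of ischemic-stroke terms, plus unspecified cerebrovascular accident terms reviewed for ischemic cause. Keep haemorrhage out of variable 11 and leave fatal haemorrhage under cardiovascular death.
3. In the Cox model, use the date of death for a fatal event with no onset date. For other undated events, state a rule so that the participant is not treated as event-free; for example, repeat the analysis with the event placed at the last event-free visit and at the reporting visit. Bounds are preferable to a single midpoint because the Day 90 and Day 270 visits are 180 days apart.

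The cost is SAP wording and programming. If the CRF holds no MACE classification, add confirmation of the term-search hits, ideally before database lock. No change to visits or sample size is needed.
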